### **3.2.3. FACT-ES**

Quality of Life Data will be reported based on the FACT-ES self-report measure, which includes five subscale domains:

- physical well-being (PWB, 7 items, score of 0-28)
- social/family well-being (SWB, 7 items, score of 0-28)
- emotional well-being (EWB, 6 items, score of 0-24)
- functional well-being (FWB, 7 items, score of 0-28)
- endocrine symptom subscale (ES, 19 items, score of 0-76)

Scores will be derived as follows:

- If  $>50\%$  of items have been answered within a subscale, then multiply the sum of the item scores by the number of items in the subscale, then divide by the number of items answered.
- If  $<50\%$  of items within a subscale have been answered, then the subscale will be reported as NE/missing.

It was discovered during the trial that a single question from the EWB subscale (GE4 “I feel Nervous”) was missing from the questionnaire. This was added in part way through the trial so some patients will not have available data for this specific question. EWB scores will still be derived (as described above) provided at least 50% of the EWB items are available at the time of data reporting.

Note, a higher score reflects a better QoL. Some scores need to be reversed by subtracting the score from 4 (see appendix A for details on reverse scoring for individual items)

Subscales scores as well as an overall FACT-ES total score (total of all 5 subscale scores, PWB+SWB+EWB+FWB)+ES) will be reported for the relevant timepoints. FACT-G scores will also be presented (total of PWB+SWB+EWB+FWB).

Boxplots of the subscale scores and total scores will be presented for each analysis set for the relevant time points.

The above FACT summaries will also be presented for the Stage 1 analysis set split by those with no insomnia (scores  $\geq 7$ ) versus those with insomnia (score  $\geq 8$ ).

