To assess the feasibility and experience of patients with breast cancer to input data relating to their sleep into a mobile phone application daily.	Feasibility and experience of patients using the digital sleep diary will be assessed using the UEQ.	Performed at Day 21 on all participants enrolled in Stage 2. Participants who withdrew from the study will be offered the questionnaire.
To assess safety of patients using the digital sleep diary.	Numbers of AEs and SAEs.	Participants will be asked to report any AEs experienced during the three-week observational period at Day 21 in a telephone consultation with the study team.
To determine associations between severity of insomnia and clinical or treatment characteristics of breast cancer patients.	Assessment of insomnia prevalence, severity, and quality of life in subgroups based on clinical/treatment characteristics including breast cancer stage, treatment regime and baseline insomnia severity.	Performed on data collected at Stage 1 and across Stage 2.

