#### **3.2.2. EQ-5D-5L**

The EQ-5D-5L descriptive system consists of five health dimensions: mobility, self care, usual activities, pain/discomfort and anxiety/depression. Patient's rate each of the dimensions on five levels: no problems, slight problems, moderate problems, severe problems, and extreme problems and these are scored 1 to 5 to give an overall 5-digit health state. For example, state 11111 indicates no problems on any of the 5 dimensions, while state 12345 indicates no problems with mobility, slight problems with washing or dressing, moderate problems with doing usual activities, severe pain or discomfort and extreme anxiety or depression

The EQ-5D-5L also uses a visual analog scale (VAS) where patients rate their health on a vertical scale from 0-100. The data from the VAS can be used as a quantitative measure of health as judged by the individual patients.

For each of the 5 dimensions, data will be reported descriptively as the number and % of patient reporting each level within the 5 dimensions. In addition, a bar chart will also be produced to graphically represent the data.

Statistical Analysis Plan for CLM-INS-004

Version: Final 2.0

Date: 9th September 2022

Data from the VAS will be summarised descriptively as a continuous variable (N, mean, median, min max etc).

The above EQ-5D-5L summaries will also be presented for the Stage 1 analysis set split by those with no insomnia (scores  $\geq 7$ ) versus those with insomnia (score  $\geq 8$ ).

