### **3.6. Association of breast cancer characteristics and sleep**

To assess any association with treatment/clinical characteristics and insomnia severity, sleep efficiency and Quality of Life, data will be reported and summarized by the following characteristics for the stage 2 analysis set:

- Breast cancer stage
  - Stage I, II or III
- Treatment regime
  - Systemic, dexamethasone, radiotherapy, hormonal or targeted
- Prior chemotherapy
  - No prior chemotherapy
  - Prior chemotherapy started  $\leq$  3 months of study entry
  - Prior chemotherapy started  $>3$  and  $\leq$  6 months of study entry
  - Prior chemotherapy started  $>$  6 months of study entry
- Baseline insomnia severity
  - subthreshold, moderate, and severe
  - Note no patient should have category of “none” for the baseline assessment since they have to have insomnia to be eligible for Stage 2

The following summary tables will be presented for the above baseline/disease characteristics:

- Insomnia severity at baseline and day 21 (for breast cancer stage, treatment and prior chemotherapy only)
- Sleep efficiency % (average of last 2 weeks)
- EQ-5D-5L, summary of 5 dimensions and VAS at baseline and day 21
- FACT-ES subscale scores, FACT-G and total-ES score at baseline and day 21

In addition to tabular summarises the following plots will be produced

- Bar charts of insomnia severity (for stage, treatment and prior chemotherapy only)
- Line plots of mean daily sleep efficiency (%) over time

Statistical Analysis Plan for CLM-INS-004

Version: Final 2.0

Date: 9th September 2022

- Boxplots of FACT-ES subscale scores, FACT-G and total-ES score at baseline and day 21

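### Baseline quality of life by insomnia severity is tabulated only in the Stage 2 set, although the four ISI bands and both quality-of-life instruments are available for the whole Stage 1 cohort

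*SAP*

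**What the plan says.** Protocol 10.3.3 plans to summarise quality of life by cancer stage, treatment regimen and baseline insomnia severity, and does not limit this to Stage 2. Protocol 3.5 gives the timing of the association objective as "Performed on data collected at Stage 1 and across Stage 2".

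The SAP handles this in two places.

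- **SAP 3.6 (Stage 2).** For the association analyses, "data will be reported and summarized by the following characteristics for the stage 2 analysis set". The baseline severity categories are "subthreshold, moderate, and severe". The SAP adds that nobody should be in the lowest category "for the baseline assessment since they have to have insomnia to be eligible for Stage 2". The tables include "EQ-5D-5L, summary of 5 dimensions and VAS at baseline and day 21" and "FACT-ES subscale scores, FACT-G and total-ES score at baseline and day 21".
- **SAP 3.2.2 and 3.2.3 (Stage 1).** "The above EQ-5D-5L summaries will also be presented for the Stage 1 analysis set split by those with no insomnia" versus those with insomnia, and likewise "The above FACT summaries will also be presented for the Stage 1 analysis set split by those with no insomnia" versus those with insomnia. No further division by severity is planned.

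SAP 3.2.1 does use all four ISI bands (0-7, 8-14, 15-21, 22-28) in Stage 1, but only to count patients.

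**The concern.** SAP 3.6 restricts all its characteristics to Stage 2. For cancer stage and treatment there is a reason: Protocol 7.4.4 has those data captured only after Stage 2 consent. The reason does not extend to ISI severity. The assessment schedule puts the ISI and both quality-of-life instruments on Stage 1 Day 0, and SAP 2.3 takes that assessment as the questionnaire baseline. So the baseline columns of the SAP 3.6 severity tables are Stage 1 data, filtered by what happened afterwards.

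The filters are more than an ISI score. Stage 2 also requires onset or worsening of sleep disturbance since diagnosis, a suitable smartphone, no sleep apnoea, no regular night work, no breast feeding, no incompatible comorbidity and a second consent. SAP 2.2 then drops anyone with no Stage 2 data. Some of these could plausibly be related to quality of life or to severity.

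Protocol section 1 lists severity and concurrent quality of life as something Stage 1 will assess, and Protocol section 2 says the results will inform eligibility criteria for future trials. For that purpose it matters whether the burden already shows at ISI 8-14 or mainly from 15 upward. A whole-cohort contrast that pools 8-14 with 22-28 cannot show this, and the table that could show it is confined to a selected group.

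**Working it through.** **1. The plan's own figures (Protocol 10.1).** Single proportion, n = z²p(1−p)/d². With p = 0.44, d = 0.05 and 90% confidence, n = 266.7, so 267 as stated. With d = 0.06 and 95% confidence, n = 262.9, so 263, which 267 covers. For Stage 2: 100/(1 − 0.20) = 125; 125/0.44 = 284.1, so 285 as stated; 285 × 0.44 = 125.4. The figures reproduce and are not in dispute.

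**2. Who is in each table.** At 44% prevalence the Stage 1 cohort has 285 × 0.56 = 159.6, about 160 people with ISI 0-7, and about 125 with ISI of 8 or more. The SAP 3.6 severity tables can hold at most 125/285 = 44% of the cohort.

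That share is not the loss. The 160 are summarised in the Stage 1 two-group table. The loss is confined to people with ISI of 8 or more who do not reach the Stage 2 set. Since 125 is simply 285 × 0.44, the planning figures treat every one of them as eligible and so imply no such loss. They give no rate for failing the other criteria or declining consent.

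**3. Loss under assumed entry.** If a fraction f of those with ISI of 8 or more enters the Stage 2 set, with an unchanged severity mix and standard deviation, the standard error of any between-band difference is multiplied by 1/√f.

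| f (assumed) | Stage 2 set | SE multiplier |
|---|---|---|
| 1.0 | 125 | 1.00 |
| 0.8 | 100 | 1/√0.8 = 1.12 |
| 0.6 | 75 | 1/√0.6 = 1.29 |

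This covers precision only. Any distortion from selective entry would be additional and cannot be sized from the documents.

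**4. What pooling does.** As an illustration with assumed values, let quality of life fall 5 points per band from the 0-7 group. With a subthreshold/moderate/severe mix of 40/45/15%, the yes/no contrast is 0.40×5 + 0.45×10 + 0.15×15 = 8.75 points. With 70/25/5% it is 0.70×5 + 0.25×10 + 0.05×15 = 6.75. The gradient is the same; only the mix differs.

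**5. What four Stage 1 bands would give.** The documents do not split ISI of 8 or more by severity, so three splits are assumed. The 95% half-width of band minus reference, in SD units, is 1.96√(1/159.6 + 1/n_band).

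| Assumed split | n in 0-7 / 8-14 / 15-21 / 22-28 | Half-widths against 0-7 |
|---|---|---|
| 50/35/15% | 160 / 63 / 44 / 19 | 0.29 / 0.33 / 0.48 |
| 60/30/10% | 160 / 75 / 38 / 13 | 0.27 / 0.36 / 0.57 |
| 70/25/5% | 160 / 88 / 31 / 6 | 0.26 / 0.38 / 0.80 |

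The subthreshold and moderate bands would be described usefully; the severe band may be thin.

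**6. The printed split.** SAP 3.2.2 and 3.2.3 print the no-insomnia group as scores of 7 or more and the insomnia group as 8 or more. Read literally, everyone scoring 8 or above is in both groups and everyone scoring 0-6 is in neither. SAP 3.2.1 defines no clinically significant insomnia as 0-7, so the inequality sign appears to be reversed.

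**The case against.** The case for leaving the plan alone has real weight.

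- A reader might infer that the SAP breaches the protocol. The documents do not support that. The quality-of-life objective in Protocol 3.5 concerns patients with ISI of 8 or more, and no objective asks for a gradient anchored on 0-7. Protocol 3.4 (viii) sets its subgroup analyses beside a full analysis set of enrolled patients, which Protocol 10.3.3 elsewhere equates with Stage 2, and it limits them to criteria i) to iii), which leaves out FACT-ES. The baseline columns in SAP 3.6 are Stage 1 data, so the wording on timing in Protocol 3.5 is arguably met.
- A reader might infer an undeclared change. SAP section 4 does list a clarification of analysis sets, though it does not mention severity.
- A reader might infer that there is no reference group at all. There is one, in the neighbouring Stage 1 table, with the same instruments and timepoint.
- Subthreshold and clinical insomnia are compared at baseline within Stage 2, which is close to the population of a future trial.
- The plan is descriptive, so no error rate is at stake, and every figure for loss of precision rests on assumed entry.

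All of this limits the point. What stands is that nothing in data collection requires the baseline by-severity summary to depend on later eligibility, consent and data provision, and that Protocol 10.3.3 plans quality of life by severity without that restriction.

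**Conclusion.** The point holds as an avoidable restriction of a descriptive analysis. The baseline by-severity tables leave out any participant with ISI of 8 or more who does not reach the Stage 2 set, and the 0-7 group can be seen only in another table beside a pooled column.

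The size is conditional. At full Stage 2 entry no participant with ISI of 8 or more is lost, and what remains is the separation of the 0-7 group from the severity bands. At an assumed 60-80% entry, between-band standard errors are about 29% to 12% larger, given an unchanged severity mix and standard deviation. It would be wrong to read the 125 of 285 as a loss of more than half the data, because the other 160 are summarised elsewhere. Nor is the Stage 2 set necessarily a minority: that follows from the 44% planning value, and at 69%, the top of the range in Protocol 10.1, it could be a majority.

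The reversed inequality in SAP 3.2.2 and 3.2.3 is a plain error that needs correcting in any case, because it defines the only whole-cohort split.

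**What to change.** In SAP 3.2.2 and 3.2.3, present the Stage 1 Day 0 EQ-5D-5L dimensions, VAS and FACT summaries, with the FACT boxplots, by the four ISI bands of SAP 3.2.1 (0-7, 8-14, 15-21, 22-28) in the Stage 1 analysis set, beside the two-group split. In the same sentences, define no insomnia as a score of 0-7 (7 or less). Keep the SAP 3.6 Stage 2 tables for describing baseline to Day 21.

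The cost is a few words of SAP text and extra columns in tables already planned, with no new data. The one drawback is that the severe band may be small, so its counts should be shown and its summaries read with caution.

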### **3.3. Daily Sleep diary data**

The sleep diary will collect the following data daily from each participant in the stage 2 analysis set:

Statistical Analysis Plan for CLM-INS-004

Version: Final 2.0

Date: 9th September 2022

1. what time the patient got into bed last night
2. what time did the patient try to go to sleep last night
3. how long it took the patient to fall asleep
4. how many times the patient woke up last night
5. in total, how long the patient was awake during the night
6. what was the patient's final wake-up time that morning
7. how long the patient stayed in bed after waking up
8. how did the patient rate their quality of sleep last night
9. did something in particular affect the patient's sleep

To determine sleep efficiency, the % of time a participant is asleep whilst in bed will be derived based on total time asleep relative to total time in bed, derived as:

- (Number of hours asleep/number of hours in bed)\*100%
  - Number of hours in bed will be derived as:
    - (Wake up time – time participant got into bed) + time in bed after waking
  - Number of hours asleep will be derived as :
    - (Wake up time – time participant got into bed)-(time to fall asleep + total time patient was awake in the night)

Sleep efficiency will be derived and assessed over the last 2 weeks of the 3-week observation period to correspond with the insomnia severity assessment which is also based on the last 2 weeks.

For each patient, a daily % will be derived and then this will be averaged over the 2 weeks. The average scores will then be summarised over time for patients in the stage 2 analysis set. Averages will be derived based on the number of days with evaluable sleep efficiency data within the 2-week period.

In addition, weekly averages will also be reported where each patient will have a weekly average derived over week 1-3 based on number of days with evaluable data within each weekly period.

Line plots of mean daily sleep efficiency (%) over time will also be presented with error bars, to allow each average daily change to be visualised.

In addition, the following information will be summarised from the sleep diary data over the last 2 weeks and also weekly for week 1-3 and plotted based on daily means across the patients:

- Time to get to sleep
- Total awake time
- Number of awakenings

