8 DIGITAL SLEEP DIARY

8.1 Description of digital sleep diary

The digital sleep diary has been designed by Closed Loop Medicine Ltd. This diary will be hosted, monitored, and managed by the digital sleep diary designers at Closed Loop Medicine. The digital sleep diary comes in the form of a patient-facing mobile phone application intended to be installed on the participant's smartphone. The application will be available in both iOS and Android, and we will establish a list of supported operating systems. A risk-based approach will be taken for supporting updates to these versions over the course of the study. All sleep data will be collected in the app. The sleep diary question set is consistent with previously published sleep diaries²⁴⁻²⁸ and will collect the following data daily from each participant:

- what time the patient got into bed last night
- what time did the patient try to go to sleep last night
- how long it took the patient to fall asleep
- how many times the patient woke up last night
- in total, how long the patient was awake during the night
- what was the patient's final wake-up time that morning
- how long the patient stayed in bed after waking up
- how did the patient rate their quality of sleep last night
- did something in particular affect the patient's sleep

No recommendations regarding diagnosis, intervention, treatment, or care planning will be made by the app.

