## Statistical Analysis Plan for CLM-INS-004

Version: Final 2.0

Date: 9th September 2022

- Quality of sleep rating (rated 1 (awful) to 10 (excellent))

Compliance of entry into the digital sleep diary will be assessed as follows:

- Entry compliance: Number and % of patients who used the diary at least once (i.e entered at least one data point into the diary)
- Completion compliance: Number and % of participants completing the digital sleep diary on at least 17 out of 21 days.
- Overall diary compliance rate derived as:
  - (number of days sleep diary completed/21)\*100%

Sleep diary data will be listed and summarized based on the stage 2 analysis set only. If any sleep variables cannot be determined at a timepoint (due to partial/missing data) then relevant variables will be considered missing at the affected timepoint(s) and excluded from the relevant data summaries.

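### SAP 3.3 starts hours asleep at getting into bed and ignores the time of the sleep attempt, so if time to fall asleep runs from the attempt, waking time in bed is counted as sleep

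*SAP*

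**What the plan says.** SAP 3.3 and Protocol 8.1 list the same nine diary questions. Item 1 is the clock time of getting into bed. Item 2 is a separate clock time, "what time did the patient try to go to sleep last night". Item 3 is "how long it took the patient to fall asleep", with no start point given. Item 4 counts awakenings. Item 5 is "in total, how long the patient was awake during the night", with no statement that it begins at sleep onset. Item 6 is the final wake-up time and item 7 the time spent in bed after it.

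SAP 3.3 describes sleep efficiency as "the % of time a participant is asleep whilst in bed". Hours in bed are item 6 minus item 1, plus item 7. Hours asleep are "Wake up time – time participant got into bed)-(time to fall asleep + total time patient was awake in the night", that is, (item 6 − item 1) − (item 3 + item 5). Item 2 enters neither formula.

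Nothing elsewhere fills the gap. Protocol 3.4 and 10.3.3 define efficiency only as a ratio of sleep time to time in bed, and SAP section 4 lists no related change.

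**The concern.** The formula returns time asleep only if items 3 and 5 together account once for every waking minute between getting into bed and the final wake-up. Someone who gets into bed, reads for half an hour and then tries to sleep has waking time that belongs to neither item, if item 3 starts at the attempt and item 5 starts at sleep onset. The formula leaves that half hour in the numerator, contrary to the SAP's own description of the measure.

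Sleep efficiency is a named secondary endpoint. The derivation feeds the two-week and weekly averages and the daily plots in SAP 3.3. In SAP 3.6 it feeds the subgroup table "Sleep efficiency % (average of last 2 weeks" and the subgroup line plots. No test or cut-off is attached, so the reported level is itself the result. SAP 3.3 does not summarise item 2, so the tables would not reveal the problem.

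**Working it through.** The documents give no sleep-efficiency figure to reproduce, so the check is algebraic.

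**Notation.** B = into bed (item 1), T = sleep attempt (item 2), W = final wake-up (item 6), G = T − B, L = minutes from the attempt to sleep onset, A = minutes awake after onset, TIB = (W − B) + item 7.

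**True sleep** = (W − B) − G − L − A. **SAP sleep** = (W − B) − (item 3 + item 5).

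The SAP sums items 3 and 5, which makes sense only if they do not overlap. Item 5 also follows the question on awakenings. I therefore take item 5 = A, and two cases remain:

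- Item 3 timed from the attempt (item 3 = L): SAP sleep − true sleep = G, so efficiency is overstated by 100 × G / TIB.
- Item 3 timed from getting into bed (item 3 = G + L): the difference is 0 and the SAP formula is right.

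**Illustration.** Every input is assumed: W − B = 540 min, item 7 = 30 min (TIB = 570), L = 30, A = 60. With item 3 timed from the attempt, the SAP value is (540 − 90)/570 = 450/570 = 78.9% whatever item 2 says.

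| Gap G (min) | True sleep (min) | True efficiency | SAP efficiency | Overstatement (points) |
|---|---|---|---|---|
| 0 | 450 | 78.9% | 78.9% | 0 |
| 15 | 435 | 76.3% | 78.9% | 2.6 |
| 30 | 420 | 73.7% | 78.9% | 5.3 |
| 60 | 390 | 68.4% | 78.9% | 10.5 |

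A 30-min gap gives 30/480 = 6.3 points at 480 min in bed and 30/600 = 5.0 points at 600 min.

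These are per-night figures. The reported value averages up to 14 nights per participant, so nights without a gap dilute it. A 30-min gap on 7 of 14 nights gives 7 × 5.3 / 14, about 2.6 points.

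**Switching to item 2 unchecked.** If item 3 in fact starts at getting into bed, (W − T) − (item 3 + item 5) removes G twice. At G = 30 that gives (510 − 60 − 60)/570 = 390/570 = 68.4% against a true 73.7%, which is 5.3 points too low.

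**Reporting both versions.** With item 5 = A, the errors of the item 1 and item 2 versions are +G and 0 if item 3 starts at the attempt, and 0 and −G if it starts at getting into bed. One of the pair is right in either case. That fails if item 5 also contains the time to fall asleep. With item 3 from the attempt, the errors become G − L and −L. At G = 15 and L = 30 they are −2.6 and −5.3 points, both too low.

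**The case against.** The strongest reply is that no error has been shown. What settles it is the app's on-screen wording, which the documents only paraphrase. If participants are asked how long they took to fall asleep after getting into bed, the formula is exact. This stands, and it makes the finding conditional.

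Nor does the non-use of item 2 prove an oversight. Item 9 enters no derivation either, and the SAP lists all data regardless. But item 2 is the only timing item the plan leaves unused, and it is asked immediately before the time to fall asleep. That makes timing from the attempt the natural reading, though not an established one.

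The sizes rest wholly on assumed gaps, and the documents give no idea how common gaps are. If a participant's gap is steady, weekly trends would barely move and mainly the level would shift. The endpoint is descriptive, and efficiency could be re-derived later because item 2 is collected and listed. All of this limits the consequence. It does not remove the need for a formula to match the definitions of its inputs.

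A reader might also infer that participants enter pre-sleep time in item 5, so that the error could shrink or reverse. Nothing in the documents suggests this, and adding items 3 and 5 points the other way.

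**Conclusion.** The point holds in conditional form. SAP 3.3 fixes a formula whose correctness depends on where item 3 starts, and neither document says. Taking item 5 as wakefulness after sleep onset, timing item 3 from the attempt overstates each night's efficiency by exactly 100 × gap / time in bed. That is 2.6 to 10.5 points for assumed gaps of 15 to 60 min at 570 min in bed. It is zero on nights without a gap, and zero throughout if item 3 is timed from getting into bed.

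A reader might conclude that the formula is simply wrong, or that reported efficiency will certainly be too high. The documents do not support that, because the start of item 3 is open and no gap data are given. Nor is the hours-in-bed denominator at fault: starting it at getting into bed matches the definition. The primary prevalence estimate and the ISI, EQ-5D-5L and FACT-ES results do not use this derivation.

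It is worth correcting because a named secondary endpoint would be misreported on the natural reading, and the data needed are already collected.

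**What to change.** Check the app's on-screen wording for two things: whether item 3 starts at the sleep attempt, and whether item 5 covers only time after sleep onset. State both in SAP 3.3. Leave hours in bed unchanged.

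- If both are confirmed, define hours asleep as (wake-up time − item 2) − (item 3 + item 5).
- If item 3 is asked from getting into bed and item 5 is post-onset, keep the formula and say so.
- If only the start of item 3 stays unclear, report efficiency from item 2 and from item 1 as a sensitivity pair. State that the pair brackets the true value only when item 5 is post-onset.

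The cost is a wording check and a line or two of SAP text and code. Reported efficiency may fall, and a few more nights may become non-evaluable because item 2 is blank. The rule at the end of SAP 3.3 already covers those nights: "If any sleep variables cannot be determined at a timepoint (due to partial/missing data) then relevant variables will be considered missing".

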10 STATISTICS AND DATA ANALYSIS

10.1 Sample size calculation

The sample size required for Stage 1 is based on an assumed prevalence of insomnia of 44% in breast cancer patients (midway point of insomnia prevalence range found in breast cancer patients 19-69%)⁴⁻¹⁰. A sample size of 267 participants is required for estimating the expected prevalence rate with 5% absolute precision and 90% confidence or 6% absolute precision and 95% confidence²⁹.

The target for Stage 2 is for approximately 100 participants to complete the study, to provide sufficient data to assess the secondary objectives. With an assumed prevalence of 44% and a 20% drop out rate, then 285 participants in Stage 1 would give an expected 125 eligible participants for Stage 2 with 100 participants assumed to complete the 3-week observation period.

Therefore, the study will aim to recruit a minimum of 285 patients into Stage 1 to cover the sample size requirements for Stage 1 and Stage 2.

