## Statistical Analysis Plan for CLM-INS-004

Version: Final 2.0

Date: 9th September 2022

The target for Stage 2 is for approximately 100 participants to complete the study, to provide sufficient data to assess the secondary objectives. With an assumed prevalence of 44% and a 20% drop out rate, then 285 participants in Stage 1 would give an expected 125 eligible participants for Stage 2 with 100 participants assumed to complete the 3-week observation period.

Therefore, the study will aim to recruit a minimum of 285 patients into Stage 1 to cover the sample size requirements for Stage 1 and Stage 2.

If the actual prevalence rate is higher than the assumed rate or the drop-out rate is lower, then the study may recruit less patients to achieve the desired 100 patients in stage 2 or the study could continue to the original recruitment target of 285 and achieve > 100 patients in stage 2. This decision will be driven by availability of patients and desired study reporting timelines ensuring the minimum target is reached.

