### **2.3. Baseline Definition**

In general, for questionnaire data, baseline is defined as the assessment completed during Stage 1 of the study on Day 0 (as indicated in Table 1).

For the sleep diary, baseline will be considered the assessment completed on Day 0 of Stage 2 (as indicated in Table 1).

Change from baseline variables will be calculated as:

- post-treatment value minus the value at baseline.

If applicable, % change from baseline will be calculated as:

- (post-baseline value - baseline value)/baseline value x 100.

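### Diary time courses and the VAS and FACT-ES summaries describe whoever has data at each time, so selective loss can look like change; only the ISI has a paired output.

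*SAP*

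**What the plan says.** **Diary (SAP 3.3).** A daily sleep-efficiency percentage is averaged within each participant over the last two weeks: "Averages will be derived based on the number of days with evaluable sleep efficiency data within the 2-week period". Weekly averages for weeks 1 to 3 follow the same rule. For the time course the plan states "Line plots of mean daily sleep efficiency (%) over time will also be presented with error bars, to allow each average daily change" to be seen. Values that cannot be determined are left out of the affected summary, and SAP 2.5 does not impute missing outcomes.

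**Quality of life (SAP 3.2.2, 3.2.3, 3.6).** The VAS is summarised as a continuous variable. For FACT-ES, "Boxplots of the subscale scores and total scores will be presented for each analysis set for the relevant time points". SAP 3 lists these instruments for the Stage 2 set at day 0 and day 21, and SAP 3.6 repeats the two-timepoint summaries by subgroup. Under SAP 2.2 the Stage 2 set keeps any consenting, eligible participant who supplied any Stage 2 data, with or without a day-21 questionnaire.

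**Change.** SAP 2.3 has a definition, introduced by "Change from baseline variables will be calculated as", but no VAS, FACT-ES or diary output in SAP 3 calls on it. The one paired display is the ISI shift table in SAP 3.2.1.

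**The concern.** Protocol 3.2 sets out to assess sleep efficiency and quality of life over three weeks in people with insomnia. A reader will compare week 1 with week 3, and baseline with day 21. Under the plan, each comparison sets one group's mean against the mean of a possibly smaller and different group. If stopping is related to how well people sleep or feel, the later mean moves because the composition changed.

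Protocol 2 and 2.1 say the results will inform later trials. A drift produced by composition could then be taken for the natural course of insomnia in these patients. The data needed to separate the two are already collected, but no planned output does so.

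**Working it through.** **1. The plan's own figures.** SAP 1.2.1 plans "With an assumed prevalence of 44% and a 20% drop out rate". Protocol 10.1 says "285 participants in Stage 1 would give an expected 125 eligible participants for Stage 2 with 100 participants assumed to complete" the observation period. Check: 285 × 0.44 = 125.4, and 125.4 × 0.8 = 100.3. Both figures reproduce. The 20% covers the whole step from eligible to completing. It is used below only as an assumed loss.

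**2. Baseline against day 21, nobody changing.** Let a proportion d of the set have no day-21 value, with mean L, and let the rest have mean R.

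- Baseline mean = (1 − d)R + dL
- Day-21 mean = R
- Apparent change = d(R − L) = d × gap

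The documents give no gap, so a range is assumed:

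| Loss d | Gap 0.25 SD | Gap 0.5 SD | Gap 1 SD |
|---|---|---|---|
| 5% | 0.013 | 0.025 | 0.05 |
| 10% | 0.025 | 0.05 | 0.10 |
| 20% | 0.05 | 0.10 | 0.20 |
| 30% | 0.075 | 0.15 | 0.30 |

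For scale, the SE of a day-21 mean with n = 100 is 1/√100 = 0.10 SD. A zero gap gives zero, and a reversed gap gives an apparent decline.

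**3. Week 3 minus week 1 sleep efficiency, nobody changing.** Simulation with 125 participants and 20% stopping. The SDs, stopping days and gaps are all assumptions.

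| Assumptions | Gap 5 points | Gap 10 points |
|---|---|---|
| Between-person SD 10, nightly SD 12, stopping on days 5 to 17 | +0.74 | +1.44 |
| Both SDs 9, stopping on days 1 to 20 | +0.67 | +1.31 |

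Hand check of the first row: 25 of 125 stop. If the last entry is equally likely on each of days 5 to 17, 3 of those 13 days fall in week 3. So 25 × 3/13 = 5.8 stoppers contribute to week 3, a share of 5.8/105.8 = 0.055 against 0.20 in week 1. The shift is (0.20 − 0.055) × 10 = 1.45 points, or 0.73 for a gap of 5.

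In the first set of assumptions the sampling SD of the available-case difference is 0.75 to 0.81 points. Restricted to people with entries in both weeks, the mean difference is about 0 in both sets, with SD about 0.65 in the first. Day 21 minus day 1 in the second set is +1.0 or +2.0, which agrees with d × gap.

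**4. Does pairing also gain precision?** If the 100 responders are among the 125 and the correlation is an assumed r = 0.7:

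- SE of the difference of the two displayed means = √(1/125 + 1/100 − 2(0.7)/125) = √0.0068 = 0.082 SD
- SE of the paired change = √(2(1 − 0.7)/100) = √0.006 = 0.077 SD

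The gain is in bias, hardly in precision.

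**5. Does the weighting of short records cause the drift?** Bias of the 2-week mean at a 10-point gap, second set of assumptions:

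- anyone with at least one night: +0.60
- at least seven nights required: +1.19
- weighted by number of nights: +1.25

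**The case against.** **What stands.** The study is observational, and these outcomes are secondary and descriptive. Protocol 10.3.3 makes the level over the last two weeks the main sleep-efficiency summary and leaves weekly values optional. Loss may be small: Protocol 7.5 seeks three-week data even from people who stop the diary, and Protocol 7.4.5 plans reminders and telephone contact. Loss should also be partly visible, because SAP 2.2 and 2.5 show missing counts where applicable, the VAS summary includes N, and SAP 3.3 reports compliance in three ways. The table templates are in a separate document that is not available. None of this supplies a same-participants comparison.

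**Stronger readings that a reader might infer, and that fail.**

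- *That the averaging rule causes the drift because one night counts as much as fourteen.* It does not. The contrast applies only to the 2-week average. Equal weight per participant costs precision there: a one-night mean has 1.2 to 1.7 times the SD of a fourteen-night mean, for assumed intraclass correlations of 0.7 to 0.3. But weighting by nights, or requiring a minimum, roughly doubles the bias (step 5).
- *That 20% of the Stage 2 set will be lost.* The 125 are expected eligible people. Some may not consent, and consenters with no Stage 2 data leave the set. Loss inside the set could be lower or higher.
- *That the plan will show false improvement.* The documents do not say that those who stop sleep or feel worse.
- *That the unpaired display wastes much precision.* Treating the two columns as independent gives √(1/125 + 1/100) = 0.134 SD, but that ignores that the same people are in both.
- *That pairing is free of bias.* It is here because the simulation lets nobody change. If people who deteriorate are the ones who stop, the paired result is biased too.

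**Conclusion.** The point holds in a limited form. The planned diary time courses and the baseline and day-21 summaries of VAS and FACT-ES can shift through changing composition alone, and SAP 2.3's change from baseline is attached to none of them.

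The size is modest and conditional. Under an assumed 20% loss, it is 0.1 SD between baseline and day 21 for a 0.5 SD gap, about as large as the SE of a day-21 mean. For week 3 minus week 1 sleep efficiency it is about 0.7 points for a 5-point gap, just under one sampling SD, and 1.4 points for a 10-point gap, nearly two. The sign follows the sign of the gap, and the shift scales with the actual loss, which is unknown.

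This is a cheap improvement to secondary descriptive outputs. The Stage 1 prevalence estimate does not depend on it.

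**What to change.** - **SAP 3.2.2, 3.2.3 and 3.6:** add within-participant change, day 21 minus baseline, with mean and 95% CI, for VAS, the FACT subscales, FACT-G and FACT-ES. Use participants with both assessments and show their own baseline beside it.
- **SAP 3.3:** add the within-participant week 3 minus week 1 difference in sleep efficiency, with mean and 95% CI, in participants with entries in both weeks. Show the number contributing at each day and week, and add a line to the plot for participants with entries in all three weeks. Week 1 is the workable reference: SAP 2.3 places the diary baseline on Stage 2 Day 0, whereas SAP Table 1 schedules entries on Days 1 to 21 and SAP 2.4 counts from the first entry as Day 1.
- **Loss:** compare baseline values of Stage 2 participants with and without day-21 data.
- **Keep** the planned raw summaries. Do not rely on a minimum-nights rule as the remedy. A mixed model for nightly sleep efficiency is optional; it rests on missing at random and would sit beside the raw summaries.

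Cost: some SAP wording and a few more tables, with no new data. The paired results describe only people with both values and stay open to bias if loss depends on change, which is why the comparison by day-21 status belongs with them.
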